# 6.1 Dose Modifications for Ramucirumab/placebo

Ramucirumab/placebo will be held for Grade  $\geq 3$  study drug related adverse events until recovery to Grade  $\leq 1$  and then resume with a dose reduction (level -1; 6 mg/kg) if site investigator evaluation relates toxicity to ramucirumab/placebo. If a second Grade  $\geq 3$  drug related adverse event is experienced and does not resolve within 2 weeks of the initial dose reduction, an additional dose reduction (level -2; 5mg/kg) will be made. If Grade  $\geq 3$  related adverse event does not resolve within 2 weeks of the second dose reduction, the subject will be taken off the trial.

Table 3. Modified dose of ramucirumab

Dose level	Ramucirumab
Starting dose	8 mg/kg
Level -1 dose reduction	6 mg/kg
Level -2 dose reduction	5 mg/kg

Version Date: 13AUG2018 Confidential Page 20 of 51

Table 4. Dosing level of ramucirumab/placebo for treatment related adverse events

Toxicity NCI	Worst Interval Toxicity	Day of Treatment
Grade (value)		
1	Maintain dose level	Continue treatment per protocol schedule.
2	Maintain dose level	Hold until resolved to grade 1 or less.
3	Reduce to dose level -1 6 mg/kg	Hold until resolved to grade 1 or less.
4	Reduce to dose level -2 5 mg/kg	Hold until resolved to grade 1 or less.

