#### 6.1.2 Proteinuria

Interrupt ramucirumab/placebo for urine protein levels  $\geq 2$  g/24 hours. Reinitiate treatment at a dose level -1 reduction (see Table 3) once the urine protein level returns to <2 g/24 hours. If the protein level  $\geq 2$  g/24 hours reoccurs, interrupt ramucirumab/placebo and reduce the dose to dose level -2 (table 4) once the urine protein level returns to <2 g/24 hours. Permanently discontinue ramucirumab if there is a third occurrence of >2 g/24 hours, or if the protein level does not return to <2 g/24 hours within 2 weeks. Permanently discontinue ramucirumab/placebo for urine protein level >3 g/24 hours or in the setting of nephrotic syndrome

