Toxicity NCI Grade	Worst Interval Toxicity	Day of Treatment
Diarrhea	G1: Maintain dose level	Hold chemotherapy if any grade
Grade 1	G2: Reduce 5-FU,	of diarrhea above baseline is
Grade 2	oxaliplatin, irinotecan 1 dose	present with the subject not
Grade 3	level	taking anti-diarrheal agents
Grade 4	G3: Reduce 5-FU,	within 24 hours of treatment.
	oxaliplatin, irinotecan 1 dose	Decrease irinotecan and
	level	oxaliplatin 1 dose level upon
	G4: Reduce 5-FU,	resolution of diarrhea. If diarrhea
	oxaliplatin, irinotecan 1 dose	has not resolved within 2 weeks
	level	of scheduled treatment day,
		discontinue therapy.

Version Date: 13AUG2018 Confidential Page 23 of 51

Table 8. Modified dosing of oxaliplatin for neurologic toxicity.

Toxicity	Du	Duration of Toxicity			
Parasthesia/dysesthesia	1-7 Days	> 7 Days	Persistent Between Doses		
Grade 1 Short duration that resolves and does not interfere with function	No change	No change	No change		
Grade 2 Interferes with function but not activities of daily living (ADL)	No change	No change	Reduce oxaliplatin 1 dose level		
Grade 3 With pain or with functional impairment that also interferes with ADL	1st time: reduce 1 dose level 2nd time: reduce another dose level	1st time: reduce 1 dose level 2nd time: reduce another dose level	Discontinue oxaliplatin		
Grade 4 Persistent symptoms that are disabling or life-threatening	Discontinue oxaliplatin	Discontinue oxaliplatin	Discontinue oxaliplatin		

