# 6.3 Protocol Therapy Discontinuation

In addition to discontinuation from therapy related to toxicities, a subject will also be discontinued from protocol therapy and followed up per protocol under the following circumstances:

- Evidence of disease progression
- The site physician thinks a change of therapy would be in the best interest of the subject
- The subject requests to discontinue protocol therapy, whether due to unacceptable toxicity or for other reasons
  - o In case a subject decides to prematurely discontinue protocol therapy ("refuses treatment"), the subject should be asked if she or he may still be contacted for further scheduled study assessments. The outcome of that discussion should be documented in both the medical records and in the eCRF.
- A female subject becomes pregnant
- If protocol therapy is interrupted for  $\geq 30$  days.

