## 11.6 Excessive Toxicity – Criteria for Stopping and Interim Safety Analysis

In case of excessive toxicity, safety-stopping rules will be used. An acceptable toxicity rate will be assumed at 0.20. The study will be stopped based on an unacceptable excessive toxicity rate of 0.40. A sequential probability ratio test will be used where a likelihood ratio of 8 in favor of an excessive toxicity rate of 0.40 (vs. 0.20) provides sufficient evidence to stop the study due to excessive toxicity. Data will be continuously reviewed for excessive toxicity and statistical analysis performed if excessive toxicity is suspected. The table below provides the minimum number of patients exhibiting excessive toxicity that will trigger statistical analysis.

Total number of treated patients	Number of Patients observed with excessive toxicity
3	≥2
4-5	≥3
6-7	≥4
8-9	≥5
10-11	≥6
12-13	≥7
14-16	≥8
17-18	≥9
19-20	≥10

Version Date: 13AUG2018 Confidential Page 41 of 51

21-23	≥11
24-25	≥12
26-28	≥13
29-30	≥14
31-33	≥15
34-35	≥16
36-38	≥17
39-40	≥18

Ramucirumab will be held for drug related adverse events Grade  $\geq 3$  until recovery to Grade  $\leq 1$  and then resumed with a lower dose level -1 (6 mg/kg). If the Grade  $\geq 3$  related adverse event does not resolve within 4 weeks of holding treatment, the subject will be taken off study treatment.

In the case of prolonged or medically concerning Grade 2 toxicity related to the chemotherapy combination, treatment will be interrupted until recovery to Grade  $\leq 1$ , at which time treatment will be resumed at the same dose. If the adverse event does not resolve in or within 2 weeks with medical intervention, then the subject will be taken off study treatment.

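### Section 6.1 and its Table 4 give different ramucirumab/placebo restart doses for a first related Grade 4 event (6 versus 5 mg/kg), and the rule for a repeat event is unclear

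*Combined protocol and SAP*

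**What the plan says.** Ramucirumab or placebo starts at 8 mg/kg every 2 weeks in 28-day cycles (section 5.1). Table 3 allows two reductions, to 6 mg/kg (level -1) and 5 mg/kg (level -2).

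**First event.** The first sentence of section 6.1 holds study drug for related events of Grade 3 or higher until they recover to Grade 1 or less, "and then resume with a dose reduction (level -1; 6 mg/kg"), if the investigator relates the toxicity to ramucirumab/placebo. It has no separate rule for Grade 4. Section 11.6 says the same, "and then resumed with a lower dose level -1 (6 mg/kg"), and the synopsis does too under Early stopping. Table 4 instead sets the dose by grade. Its Grade 3 row reads "Reduce to dose level -1 6 mg/kg" and its Grade 4 row reads "Reduce to dose level -2 5 mg/kg".

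**Repeat event.** Section 6.1 moves to 5 mg/kg if a second "drug related adverse event is experienced and does not resolve within 2 weeks of the initial dose reduction". Table 4 has no entry for a repeat event.

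**Elsewhere.** Some events have their own rules: hypertension (6.1.1), proteinuria (6.1.2), venous thromboembolism (6.1.5) and the permanent-discontinuation list (6.1.6). For proteinuria the sequence is level -1, then level -2, then "Permanently discontinue ramucirumab if there is a third occurrence". For a second Grade 3 neurologic event that does not persist between doses, Table 8 steps oxaliplatin down again: "2nd time: reduce another dose level".

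**The concern.** Grade 3 or higher includes Grade 4, so an event attributed to ramucirumab/placebo falls under both the 6.1 text and Table 4. For a first Grade 4 event the two give different doses. In a multicenter double-blind trial, two sites could each comply with the protocol and restart similar subjects on different doses of blinded study drug.

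The second problem arises after one reduction. A subject at 6 mg/kg has a further related Grade 3 event, which recovers. Depending on how the 2-week window is read, and on whether the text or the table is followed, that subject restarts at 5 mg/kg or goes back to the dose on which the toxicity recurred, although a lower level exists. At stake are the safety of subjects with serious toxicity and uniform conduct across sites.

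**Working it through.** The plan states no figure to reproduce. The check sets the rules side by side and converts the doses.

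**Scope.** The event must be related to ramucirumab/placebo in the investigator's judgement, must recover, and must not fall under a stop rule in 6.1.1, 6.1.2, 6.1.5 or 6.1.6. Neutropenia is an example. It is listed for ramucirumab in 9.1.5 and is absent from the 6.1.6 list. Table 6 reduces the three chemotherapy drugs for Grade 4 neutropenia but does not set the ramucirumab/placebo dose.

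**1. First related Grade 4 event at 8 mg/kg**

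| Source | Restart dose | Change from 8 mg/kg |
|---|---|---|
| 6.1 text | 6 mg/kg | 6/8 - 1 = -25.0% |
| 11.6 | 6 mg/kg | -25.0% |
| Synopsis | 6 mg/kg | -25.0% |
| Table 4, Grade 4 row | 5 mg/kg | 5/8 - 1 = -37.5% |

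Table 4 relative to the text: 5/6 - 1 = -16.7%.

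Per 28-day cycle, with one infusion every 2 weeks (two per cycle):
- full dose: 2 × 8 = 16 mg/kg
- 6.1 text: 2 × 6 = 12 mg/kg
- Table 4: 2 × 5 = 10 mg/kg

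No sentence gives either source precedence.

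**2. Second related Grade 3 event at 6 mg/kg that recovers**

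The window in 6.1 runs from the first dose reduction, not from the second event. That leaves two readings:

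- *Intent reading.* The window is meant to ask whether the second event resolves promptly. A repeat event that resolves quickly then triggers no step down.
- *Literal reading.* A second event that starts more than 2 weeks after the first reduction cannot resolve inside a window that has already closed, so it steps down to 5 mg/kg. Only a second event that both starts and resolves within 2 weeks of the first reduction escapes. With dosing every 2 weeks, that is about one dosing interval.

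Taken at face value, the Grade 3 row of Table 4 names 6 mg/kg whatever the current dose.

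| Second Grade 3 event at 6 mg/kg | 6.1, intent reading | 6.1, literal reading | Table 4 |
|---|---|---|---|
| Starts and resolves within 2 weeks of first reduction | no step down | no step down | 6 mg/kg |
| Starts more than 2 weeks after first reduction, resolves quickly | no step down | 5 mg/kg | 6 mg/kg |

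Returning to 6 mg/kg is a change of 6/6 - 1 = 0%. Using level -2 is 5/6 - 1 = -16.7%. In the second row the answer depends on the reading, and on the literal reading the text and the table disagree.

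**The case against.** **Table 4 may be the specific rule that refines the general text.** That is a reasonable drafting convention, but the protocol does not state it. A reader of section 11.6 or the synopsis would see only 6 mg/kg.

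**It is tempting to infer that neither rule ever steps down after a repeat Grade 3 event that resolves.** The documents do not support that. On the literal reading above, most later repeat events do go to 5 mg/kg. In addition, the first sentence of 6.1 speaks of resuming with a reduction, which going from 6 to 6 is not, and the Table 4 rows may presuppose a higher current dose. What stands is that the rule is ambiguous and that the Grade 3 row does not fit a subject already at 6 mg/kg.

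**A reader might also infer that an event at 5 mg/kg has no dose instruction, and that discontinuation must follow.** Neither inference holds. If Table 4 is read by grade alone, it does name doses there, and the Grade 3 entry would even be an increase. Section 6.1 takes a subject off the trial only if the event fails to resolve within 2 weeks of the second reduction. Otherwise 6.3 leaves it to judgement: "The site physician thinks a change of therapy would be in the best interest of the subject". Mandatory discontinuation at 5 mg/kg would be a new clinical rule. The proteinuria and oxaliplatin sequences are specific to that event and that drug, so they show a workable pattern without obliging the same general rule.

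**Few subjects may be affected.** This is fair. Neutropenia is also listed for irinotecan (9.3.3) and oxaliplatin (9.4.4), so attribution to ramucirumab is not automatic. Arm B receives placebo, so the difference in active drug arises only in Arm A.

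**Conclusion.** The conflict over a first related Grade 4 event is plain on the text: 6 mg/kg (-25%) in section 6.1, section 11.6 and the synopsis, against 5 mg/kg (-37.5%) in Table 4, or 12 against 10 mg/kg per cycle. This assumes that the event is attributed to ramucirumab/placebo, recovers, and is not under a stop rule.

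The repeat-event rule is unclear rather than shown to be absent. The window in 6.1 supports two readings, and the Grade 3 row of Table 4 names 6 mg/kg for a subject already at that dose.

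The number of subjects affected cannot be derived from the documents. A reader might infer a bias in the primary comparison. Nothing in the documents shows one, and the sample size, type 1 error and power do not depend on this rule. The change should be made on grounds of safety and consistency.

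**What to change.** 1. State one restart dose for a first related Grade 4 event at 8 mg/kg, the same in section 6.1, Table 4, section 11.6 and the synopsis. The more cautious choice is 5 mg/kg; 6 mg/kg is what three of the four places now say. The choice is the sponsor's.
2. Reword section 6.1 and Table 4 so that a related event of Grade 3 or higher at 6 mg/kg that recovers restarts at level -2 (5 mg/kg), as 6.1.2 already does for proteinuria. Remove the dependence on a window counted from the first reduction.
3. Leave 6.1.2 and the permanent-discontinuation rules as they are. What to do after a further related Grade 3 or higher event at 5 mg/kg is for the sponsor to decide.

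While these paragraphs are open, the sponsor may also want to align the limits for an event that does not resolve: 2 weeks after the second reduction in 6.1, 3 weeks of holding in the synopsis, and 4 weeks in 11.6. That is a separate matter, and the changes above do not settle it.

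The cost is two rows of Table 4, one or two sentences in 6.1, and a matching line in 11.6 and the synopsis. No visits, tests or subjects are added. The downside is a slightly lower study-drug dose in some subjects with toxicity.

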#### **6.1.1** Management of Hypertension

Interrupt ramucirumab/placebo for severe hypertension until controlled with medical management. Permanently discontinue ramucirumab/placebo for severe hypertension that cannot be controlled with antihypertensive therapy. The subject will continue to be followed per guidelines in Section 7. Subjects with grade 4 hypertension must not receive further treatment with ramucirumab

#### 6.1.2 Proteinuria

Interrupt ramucirumab/placebo for urine protein levels  $\geq 2$  g/24 hours. Reinitiate treatment at a dose level -1 reduction (see Table 3) once the urine protein level returns to <2 g/24 hours. If the protein level  $\geq 2$  g/24 hours reoccurs, interrupt ramucirumab/placebo and reduce the dose to dose level -2 (table 4) once the urine protein level returns to <2 g/24 hours. Permanently discontinue ramucirumab if there is a third occurrence of >2 g/24 hours, or if the protein level does not return to <2 g/24 hours within 2 weeks. Permanently discontinue ramucirumab/placebo for urine protein level >3 g/24 hours or in the setting of nephrotic syndrome

#### **6.1.3** Wound Healing Complications

Interrupt ramucirumab/placebo prior to scheduled surgery until the wound is fully healed

#### **6.1.4** Thyroid Dysfunction

Monitor thyroid function during treatment with ramucirumab. In Study 4, the incidence of hypothyroidism reported as an adverse event was 2.6% in the ramucirumab plus FOLFIRI treated subjects and 0.9% in the placebo plus FOLFIRI treated subjects.

#### 6.1.5 Venous Thromboembolic Events

Ramucirumab therapy should be discontinued in the event of any Grade 3/4 VTE that is considered by the site investigator to be life threatening, or symptomatic and not adequately treated by anticoagulation therapy. Patients with unresected primary tumors (or local recurrence) who develop Grade 3 and 4 venous thromboembolism may also receive anticoagulation and continue ramucirumab therapy provided that the tumor does not confer an excessive bleeding risk, in the opinion of the patient's physician. Ramucirumab should

Version Date: 13AUG2018 Confidential Page 21 of 51

also be discontinued in the setting of a deep vein thrombosis or pulmonary embolism that occurs or intensifies while the patient is receiving therapeutic anticoagulation therapy. Any venous event leading to discontinuation of ramucirumab therapy will be considered serious and should be reported via the serious adverse event (SAE) mechanism.

# 6.1.6 Conditions for permanent discontinuation of ramucirumab/placebo

Listed below are clinical conditions in which ramucirumab/placebo should be permanently discontinued.

- Grade 3 and 4 arterial thromboembolic events, or any PE/DVT occurring or
  worsening during anticoagulant therapy. Any arterial event leading to
  discontinuation of ramucirumab therapy will be considered serious and should be
  reported via the serious adverse event (SAE) mechanism.
- Subjects with Grade 4 hypertension must not receive further treatment with ramucirumab
- Gastrointestinal Perforation
- Grade 3 or 4 Bleeding
- Grade 3 or 4 Infusion Reaction
- Hepatic encephalopathy or other serious signs of liver impairment such as hepatorenal syndrome
- Fistula Formation
- Reversible Posterior Leukoencephalopathy (RPLS); All cases of RPLS must be reported via the SAE reporting guidelines.

#### **6.2 Dose Modification for mFOLFIRINOX**

Toxicities to 5-Fluorouracil (5-FU), oxaliplatin and irinotecan may include hematologic and non-hematologic events. The dose adjustment of 5-Fluorouracil, oxaliplatin, and irinotecan for hematologic toxicity is shown in Table 5.

Table 5: Modified dosing of the mFOLFIRINOX combination

Dose level	Oxaliplatin	Irinotecan	5-FU Infusion
Starting dose	85 mg/m 	165 mg/m 	2400 mg/m 
First dose reduction	50 mg/m 	150 mg/m 	1800 mg/m 
Second dose reduction	40 mg/m 	127 mg/m 	1200 mg/m 

Toxicity NCI Grade	Worst Interval Toxicity	Day of Treatment
Diarrhea	G1: Maintain dose level	Hold chemotherapy if any grade
Grade 1	G2: Reduce 5-FU,	of diarrhea above baseline is
Grade 2	oxaliplatin, irinotecan 1 dose	present with the subject not
Grade 3	level	taking anti-diarrheal agents
Grade 4	G3: Reduce 5-FU,	within 24 hours of treatment.
	oxaliplatin, irinotecan 1 dose	Decrease irinotecan and
	level	oxaliplatin 1 dose level upon
	G4: Reduce 5-FU,	resolution of diarrhea. If diarrhea
	oxaliplatin, irinotecan 1 dose	has not resolved within 2 weeks
	level	of scheduled treatment day,
		discontinue therapy.

Version Date: 13AUG2018 Confidential Page 23 of 51

Table 8. Modified dosing of oxaliplatin for neurologic toxicity.

Toxicity	Du	Duration of Toxicity			
Parasthesia/dysesthesia	1-7 Days	> 7 Days	Persistent Between Doses		
Grade 1 Short duration that resolves and does not interfere with function	No change	No change	No change		
Grade 2 Interferes with function but not activities of daily living (ADL)	No change	No change	Reduce oxaliplatin 1 dose level		
Grade 3 With pain or with functional impairment that also interferes with ADL	1st time: reduce 1 dose level 2nd time: reduce another dose level	1st time: reduce 1 dose level 2nd time: reduce another dose level	Discontinue oxaliplatin		
Grade 4 Persistent symptoms that are disabling or life-threatening	Discontinue oxaliplatin	Discontinue oxaliplatin	Discontinue oxaliplatin		

# 6.3 Protocol Therapy Discontinuation

In addition to discontinuation from therapy related to toxicities, a subject will also be discontinued from protocol therapy and followed up per protocol under the following circumstances:

- Evidence of disease progression
- The site physician thinks a change of therapy would be in the best interest of the subject
- The subject requests to discontinue protocol therapy, whether due to unacceptable toxicity or for other reasons
  - o In case a subject decides to prematurely discontinue protocol therapy ("refuses treatment"), the subject should be asked if she or he may still be contacted for further scheduled study assessments. The outcome of that discussion should be documented in both the medical records and in the eCRF.
- A female subject becomes pregnant
- If protocol therapy is interrupted for  $\geq 30$  days.

# 6.4 Study Withdrawal

If a subject decides to withdraw from the study (and not just from protocol therapy) all efforts should be made to complete and report study assessments as thoroughly as possible. The site investigator should contact the subject or a responsible relative by telephone or through a personal visit to establish as completely as possible the reason for the study withdrawal. A complete final evaluation at the time of the subject's study withdrawal should be made with an explanation of why the subject is withdrawing from the study. If the reason for removal of a subject from the study is an adverse event, it will be recorded on the eCRF.

Version Date: 13AUG2018 Confidential Page 24 of 51

# HCRN GI14-198 Clinical Study Protocol

# 7. STUDY CALENDAR & EVALUATIONS

# CYCLE = 28 DAYS

	Screening	Cycl	le 1–2	Cycl	e 3–4	Cyc	le 5+	End of Treatment Visit	Follow up
Examination	Within 28 days of registration	Day 1 (±7)	Day 15 (±3)	Day 1 (±3)	Day 15 (±3)	Day 1 (±3)	Day 15 (±3)	30 days (± 7) after last dose of study drug	
REQUIRED ASSESSMENTS									
Demographics and Medical History/Height	X								
Physical Examination	X	X	X	X	X	X	X	X	
Vital Signs and ECOG PS 	X	X	X	X	X	X	X	X	
Comprehensive Metabolic Panel 	X	X	X	X	X	X	X	X	
Magnesium and uric acid	X	X	X	X	X	X	X	X	
CBC with Differential and platelet 	X	X	X	X	X	X	X	X	
PT, PTT, INR 	X								
CA19-9 	X	X		X		X			
Pregnancy Test (Urine or Serum β-HCG) 	X								
Urinalysis 	X	X		X		X			
AEs and Con Meds	X	X	X	X	X	X	X	X	
Thyroid function (TSH, total T 3 , free T 4 ) 	X		X		X		X		
Diagnosis Confirmation 	X								
DISEASE ASSESSMENT									
CT or MRI of Chest, Abdomen and Pelvis 	X			X		X		X	$X^9$
TREATMENT									
mFOLFIRINOX every 2 weeks		X	X	X	X	X	X		
Ramucirumab/placebo every 2 weeks		X	X	X	X	X	X		
FOLLOW-UP									
For progression, start of additional cancer treatment, and survival 									X 

- 1: Vital signs to include blood pressure, weight, height (screen only) and ECOG performance status.
- 2: CMP to include Sodium, potassium, total bilirubin, alkaline phosphatase, alanine aminotransferase (ALT), aspartate aminotransferase (AST), blood urea nitrogen (BUN), creatinine, calcium, random glucose, albumin
- 3: CBC to include Hemoglobin, hematocrit, erythrocyte count (RBC), mean cell volume, mean cell hemoglobin concentration, leukocytes (WBC), neutrophils, lymphocytes, monocytes, basophils, platelets
- 4: CA19-9 at screening and every 2 cycles
- 5: Serum pregnancy test for women of child-bearing potential must be performed within 7 days prior to first dose of study treatment
- 6: Protein in the urine should be monitored prior to each cycle. Urine dipstick may be used to quantify the amount if necessary.
- 7: Confirmation of diagnosis must be obtained during screening. A pathology report with staging information will be obtained from the institution that performed the diagnosis procedure.
- 8: Scans to be repeated every 8 weeks (± 7 days) until progression of disease. Pre-treatment scans to be performed within 28 days prior to registration.
- 9: For subjects who discontinue study treatment without radiographically documented PD, the investigative sites will continue to evaluate tumor response every 8 weeks ( $\pm$  7 days) by the same method used at baseline and throughout the study until time of disease progression, death or until study completion, except when not feasible in the opinion of the site investigator due to subject's clinical status. After the subject has documented PD, radiologic assessments are no longer required and the subject will be followed every 8 weeks ( $\pm$  7 days) until the subject's death or study completion, whichever is earlier.
- 10: If the TSH is abnormal, a total T3 and free T4 should be ordered.
- 11: Coagulation tests should be periodically repeated during the course of the study per site investigator discretion.

